Transfusion history and status; myeloid growth factor treatment	Assessment of RBC transfusion requirements and myeloid growth factor use 16 weeks prior to randomization, at each 4-week cycle visit, disease evaluation visit, and all unscheduled visits during treatment. Complete transfusion information must be collected, including both in-patient and out-patient transfusions	X	X ^a		Only Day 1 ^a	Only Day 1 ^a	Only Day 1 ^a	X	X (first visit and every 4-6 weeks if feasible)

TIME AND EVENTS SCHEDULE - DARATUMUMAB

PHASE	Study Procedures	Notes	Screening Phase	Treatment Phase (4-week cycles +/-3 days)					Posttreatment Follow-up Phase	
			Up to 28 days before first dose	Cycle 1 Day 1	Cycle 1 Day 8, 15, 22	Cycle 2 Day 1, 8, 15, 22	Cycle 3, 4, 5, 6 Day 1, 15	Cycle 7 until EOT Day 1	EOT Visit Within 30 days after last dose	Survival Follow-up Every 16 weeks (+/- 7 days)
	Bone marrow aspirate with cytogenetics and bone marrow biopsy	Bone marrow aspirate and biopsy with iron stain must be performed during screening or up to 12 weeks prior to first dose. Following the bone marrow at PR and CR, bone marrow should be repeated 4 to 8 weeks later for confirmatory purposes. The EOT bone marrow does not have to be performed if the prior assessment occurred within 8 weeks. Bone marrow assessments can be performed within a window of ± 7 days.	X	Every 24 weeks, at time of PR, CR, and at PD If PR/CR occurs, a bone marrow is collected every 24 weeks thereafter					X	
	Response assessment	Per IWG 2006		Week 12, 24, 36, 48, 60, 72 and then every 24 weeks until PD					X	
	ECOG performance status		X	X ^a		Only Day 1 ^a	Only Day 1 ^a	X ^a	X	
	Survival status									X
	Biomarker Assessments									
	Bone marrow biopsy	See Efficacy Assessments Section	X							
	Bone marrow aspirate	See Efficacy Assessments Section	X	At time of suspected PR/CR and every 24 weeks thereafter until PD					X (or PD)	
	Peripheral blood	Peripheral blood will be collected at specified visits and at the time of PR/CR and every 24 weeks thereafter. Immunophenotyping will be performed by flow cytometry and CyTOF.		X ^a	Only Day 15 ^a	Only Day 1 ^a	Only Day 1 of Cycles 4 and 6 ^a		X (or PD)	
	Plasma	Plasma will also be collected at specified visits and at the time of PR/CR and every 24 weeks thereafter.		X ^a			Only Day 1 of Cycle 4 ^a		X (or PD)	

TIME AND EVENTS SCHEDULE - DARATUMUMAB

PHASE	Notes	Screening Phase	Treatment Phase (4-week cycles +/-3 days)						Posttreatment Follow-up Phase

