The standard prognostic tool in MDS is the International Prognostic Scoring System (IPSS), which classifies patients into low, intermediate-1, intermediate-2, and high risk categories on the basis of the percentage of bone marrow blasts, the karyotype, and the number of cytopenias. The median survival rates for the low, intermediate-1, intermediate-2, and high risk categories are estimated at 5.7, 3.5, 1.2, and 0.4 years, respectively.^{3,7} Other prognostic systems have also been described, namely the WHO classification-based Prognostic Scoring System (WPSS)²⁵ and IPSS-Revised (IPSS-R).⁸ The IPSS is more frequently referenced in clinical trials. Patients with low and intermediate-1 risk MDS are also often referred to as having “lower risk” disease, whereas those with intermediate-2 and high risk MDS are referred to as patients with “higher risk” disease.

Treatment Options for MDS

For patients with IPSS low and intermediate-1 risk MDS, the initial approach to treatment typically involves supportive care measures, ie, red blood cell (RBC) transfusions or erythropoiesis-stimulating agents (ESAs) or other hematopoietic growth factors, aimed at alleviating cytopenias. Approximately 40% of the patients will achieve an International Working Group (IWG)-defined hematologic improvement to ESAs for a median duration of 2 years. The Nordic MDS group has developed a model that identifies patients more likely to respond to ESAs. Those with low or no transfusion requirements (<2 packed red blood cell [pRBC] units/month) and a low serum erythropoietin (EPO) level (<500 units/L) have a higher response

rate than those with high transfusion needs (≥ 2 units/month) and serum EPO level (≥ 500 units/L); 74% versus 7%, respectively.¹⁰

A marker of disease severity appears to be associated with early ESA failure (no response to ESA or relapse within 6 months). Patients whose disease fails ESA early compared to later failure have a higher rate of transformation to acute myeloid leukemia (AML) (5-year cumulative incidence of 22% versus 9%, respectively; $p=0.02$) with a much shorter median overall survival (OS) (37 months versus 54 months, respectively; $p=0.02$).¹⁵ This median survival is considerably shorter than predicted at the time of diagnosis.

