The rate of HI-E will provide further explanation of the hematologic response (as per IWG criteria). Progression to AML and OS are important endpoints considering that the natural history of MDS progression includes transformation to AML in a proportion of patients.

The depth of the response will be captured by assessment of CR and PR. Duration of responses will be assessed. Subjects will be followed for OS.

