9.2.3. Clinical Bone Marrow Assessment

Bone marrow aspirate and biopsy must be performed during screening or up to 12 weeks before randomization. Follow-up bone marrow exams will be performed every 24 weeks, at the time of PR and CR (as indicated by peripheral blood counts), at disease progression, and at end-of-treatment. Following the bone marrow exams at PR and CR, bone marrow sampling should be repeated 4 to 8 weeks later. Bone marrow sampling does not have to be repeated at the End-of-Treatment visit if the prior assessment occurred within 8 weeks.

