13 (43.3)	(32.3, 55.0)	
14 (46.7)	(35.4, 58.2)	

¹ Using $B(0.5, 0.5)$ as the prior distribution for true IT rate

² With false negative error rate <10%; ie, when observing number of TI ≤ 5 , there is a <10% chance that the true TI rate is $\geq 30\%$

³ With false positive error rate <10%; ie, when observing number of TI ≥ 8 , there is a <10% chance that the true TI rate is $\leq 15\%$

In addition to the aforementioned statistical assessments, sensitivity analyses will also be performed for the primary endpoint. In these analyses, additional subjects will also be considered transfusion independent if they are transfusion-free for less than 8 weeks but have maintained such a status for at least 6 consecutive weeks (42 days) by the time of the clinical cutoff (6 months after last randomization).

Secondary Endpoints

The proportion of subjects with TI lasting at least 168 days (24 weeks), CR, PR, and HI will be summarized descriptively.

The distributions of time to TI, and duration of TI will be estimated for each treatment arm using Kaplan-Meier method. These analyses will be based on subjects who achieve TI.

Other time-to-event endpoints including OS and time to progression to AML will be analyzed using Kaplan-Meier methods.

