6. EFFICACY

6.1. PRIMARY EFFICACY ENDPOINT

6.1.1. DEFINITION

The primary efficacy endpoint is the rate of RBC TI lasting for at least 8 weeks. The 8-week RBC TI rate is defined as the proportion of subjects without any RBC transfusion during any consecutive 8 weeks (56 days) starting from Study Day 1 until the end of study. The starting date of 8-week RBC TI must be between Study Day 1 and End of treatment Phase ending date (date of last dose of study medication + 30 days).

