Time to progression to AML is defined as the interval from Study Day 1 to the date of AML progression (bone marrow or peripheral blood blasts $\geq 20\%$). Subjects who have not progressed to AML at the cutoff date for the analysis or who withdraw from the study will be censored at the date of the last disease evaluation.

Amount and Relative Change in RBC Transfusions

Amount of RBC transfusions is defined as the total number of RBC transfusion units in a given post-baseline 8-week (any consecutive 56 days period) interval during study. The starting date of a post-baseline 8-week interval must be between Study Day 1 and End of treatment Phase ending date (date of last dose of study medication + 30 days). Relative change in RBC transfusions is defined as:

$$\text{Relative change in RBC Transfusion} = \frac{\text{amount of RBC transfusions} - \text{prior RBC transfusion burden}}{\text{prior RBC transfusion burden}} * 100 \%$$

Note that prior RBC transfusion burden is the maximum number of RBC units transfused over an 8-week period during the 16 weeks prior to Study Entry.

The best RBC transfusion reduction is defined as the “best” or the “minimum” number of RBC transfusions in any post-baseline 8-week interval. The time to the best transfusion reduction in an 8-week interval (in weeks), the minimum number of RBC transfusions received during this interval, and the relative change from baseline will be summarized.

Rate and Duration of Myeloid Growth Factor Usage

Rate of myeloid growth factor usage is defined as the proportion of subjects receiving any myeloid growth factors starting from Study Day 1; duration of myeloid growth factor administered starting from Study Day 1.

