6.2.2. ANALYSIS METHODS

Rate of 24-week TI, CR, PR, and hematologic improvement (HI), and other binary endpoints, will be summarized with percentage along with its 95% 2-sided exact Clopper-Pearson confidence interval.

The time to 8-week RBC TI and time to 24-week RBC TI will be summarized descriptively.

The Kaplan-Meier method will be used to estimate the distribution of duration of RBC TI for 8-week and 24-week TI responders, respectively. The distribution of OS and time to progression to AML will be summarized using similar Kaplan-Meier methods.

Amount and relative change in RBC transfusions will be summarized descriptively by time point.

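### Time to AML: deaths without AML are censored by default, so one minus Kaplan-Meier slightly overstates the proportion who develop AML (minor)

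*SAP*

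**What the plan says.** SAP 6.2.1 measures time to progression to AML from Study Day 1 to the date when marrow or blood blasts reach 20%. Subjects without AML at the analysis cutoff, and those who withdraw, "will be censored at the date of the last disease evaluation". Death is not named here; it is an event only for overall survival.

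On the estimator, SAP 6.2.2 states: "The distribution of OS and time to progression to AML will be summarized using similar Kaplan-Meier methods". Protocol 11.3 agrees: "Other time-to-event endpoints including OS and time to progression to AML will be analyzed using Kaplan-Meier methods". Neither document plans a competing-event rule or a cumulative incidence estimate.

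Two passages show how the endpoint is likely to be read. Protocol 3.2 justifies it because the "natural history of MDS progression includes transformation to AML in a proportion of patients". The Protocol's Introduction gives the background AML risk after early versus later ESA failure as a "5-year cumulative incidence of 22% versus 9%, respectively".

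On ascertainment, the daratumumab Time and Events Schedule places response assessment at "Week 12, 24, 36, 48, 60, 72 and then every 24 weeks until PD", plus the end-of-treatment visit. Protocol 9.2.3 schedules marrow every 24 weeks, at response, "at disease progression, and at end-of-treatment". The survival follow-up column contains no marrow, hematology or response assessment.

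**The concern.** A subject who has died cannot later develop AML. Kaplan-Meier with such deaths censored describes AML in a hypothetical setting where nobody dies first. That is a legitimate summary of the cause-specific hazard, but it is not the share of subjects who transform. One minus Kaplan-Meier exceeds that share whenever AML events follow AML-free deaths.

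The dating rule works in the same direction. Censoring a death at the preceding disease evaluation removes the subject from the risk set before the death occurred. Each later AML event is then divided by a smaller number at risk, so the estimate can only stay the same or rise.

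At stake is a reader's ability to set the trial's AML figure beside the cumulative incidences in the Introduction. No decision rule depends on it.

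**Working it through.** The documents state no planned AML figure, so there is nothing to reproduce. The size is estimated from the Protocol's own background rates.

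**Inputs (Protocol 1, Introduction).** Early ESA failure: median OS 37 months, 5-year AML incidence F = 22%. Later failure: 54 months, F = 9%. N = 30 (SAP 3.3). Data collection ends 1 year after the last randomization (Protocol 9.1.5), so only subjects randomized at least a year before the last one can reach 24 months.

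**Assumptions.** Constant monthly hazards, h for AML and d for death without AML. The background incidences are taken as competing-risk incidences. Everyone is followed for both events.

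**Formulas.**
- Overall death hazard L = ln 2 / median OS: 0.6931/37 = 0.01873 (early); 0.6931/54 = 0.01284 (later).
- Cumulative incidence: CIF(t) = h/(h+d) × [1 − exp(−(h+d)t)].
- Kaplan-Meier with deaths censored: 1−KM(t) = 1 − exp(−ht).

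**Bracketing d.**
- Low end, AML fatal at once: h + d = L, so h = F·L/[1 − exp(−60L)]. Early: 0.22 × 0.01873/0.6750 = 0.00611, so d = 0.01263 (67% of L). Later: 0.09 × 0.01284/0.5371 = 0.00215, so d = 0.01069 (83% of L).
- High end, AML adds no mortality: d = L, with h solved so that CIF(60) = F. Early: h = 0.00724. Later: h = 0.00228.

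**Worked line (early, low end, 12 months).** 1−KM = 1 − exp(−0.00611 × 12) = 7.06%. CIF = (0.00611/0.01873) × [1 − exp(−0.01873 × 12)] = 0.326 × 0.201 = 6.56%. The gap is 0.50 points.

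| Background, end of range | 12 mo: 1−KM vs CIF | Gap | 24 mo: 1−KM vs CIF | Gap |
|---|---|---|---|---|
| Early, low d | 7.06% vs 6.56% | 0.50 | 13.63% vs 11.80% | 1.83 |
| Early, high d | 8.32% vs 7.46% | 0.86 | 15.94% vs 12.92% | 3.02 |
| Later, low d | 2.55% vs 2.39% | 0.16 | 5.03% vs 4.44% | 0.59 |
| Later, high d | 2.70% vs 2.50% | 0.20 | 5.33% vs 4.59% | 0.74 |

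Expected among 30 subjects by 12 months: 0.7 to 2.2 AML cases and 3.6 to 5.8 AML-free deaths.

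**Check without a hazard model.** Take 30 subjects with 2 AML cases, 4 AML-free deaths and otherwise complete follow-up. Cumulative incidence is 2/30 = 6.7%. If both AML cases precede every death, 1−KM is also 6.7%. If both follow all four deaths, it is 1 − (25/26)(24/25) = 7.7%.

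**Against sampling error.** The exact 95% interval for 2/30 is 0.8% to 22.1%, about 21 points wide.

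**The case against.** **The SAP never claims that 1−KM is a probability of AML.** True. It promises the distribution of a time to event, Kaplan-Meier is valid for the cause-specific hazard, and the Introduction's rates are background, not an estimand. What remains is how the curve will be read: the Protocol itself speaks of a proportion and a cumulative incidence.

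**The sizing assumes full follow-up.** This stands as a limit. If observation ended at about 7 months (an assumption), the same hazards give a gap of 0.05 to 0.31 points. A related argument is that under literal last-evaluation censoring no death enters, so a cumulative incidence estimate would equal 1−KM and nothing is overstated. That does not hold. It compares 1−KM with an estimator carrying the same fault, not with the true incidence.

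**A stronger reading.** A reader might infer that the SAP leaves open whether AML found after end of treatment counts, and that observation should stop at last dose + 30 days. The documents do not support this. For transfusion independence the SAP ties the start of the qualifying period to the "End of treatment Phase ending date (date of last dose of study medication + 30 days"). The AML definition has no such limit and runs to the analysis cutoff. Its natural reading is that AML with documented blasts of at least 20% counts whenever it occurs. Truncation would discard such events and narrow the endpoint. Nor would it yield the proportion observed on treatment: with no deaths, 24 of 30 leaving AML-free and censored, and one later AML among the 6 who stay, the estimator gives 1/6 = 16.7% against an observed 1/30 = 3.3%.

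**Conclusion.** The point holds and is minor. By default AML-free deaths are censored at the last disease evaluation. Read as the proportion developing AML, 1−KM is then too high by about 0.2 to 0.9 points at 12 months and 0.6 to 3.0 at 24 months. These figures rest on the Protocol's background rates, constant hazards and full follow-up; they are for sizing only and do not predict this trial.

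A reader should not infer that the AML result would be materially misleading. The endpoint is descriptive, only the daratumumab arm is analysed (SAP 3.6), the gap is small beside the sampling error, and the primary decision is untouched. The case for the change is its low cost.

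**What to change.** **SAP 6.2.1.** Define death without AML as a competing event dated at death, not as censoring at the last disease evaluation. The date matters: if each subject's observation stopped at the last evaluation, no death would enter and the new estimate would equal 1−KM. Keep the present event definition, with AML with documented blasts of at least 20% counting up to the analysis cutoff, on or off treatment. List separately any AML known only from subsequent therapy or cause of death. Do not truncate at last dose + 30 days.

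**SAP 6.2.2.** Report the Aalen-Johansen cumulative incidence of AML with a 95% confidence interval. Beside it, give the crude number and percent with documented AML (n/N, Clopper-Pearson). Keep Kaplan-Meier as a cause-specific supplement, which still delivers what Protocol 11.3 promises.

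**Downside to state.** With no blast or marrow assessment scheduled after the end-of-treatment visit, AML-free leavers are censored at about that visit, while their later deaths or AML can still be recorded. This can bias the estimate either way:
- Too high: suppose there are no deaths, 15 to 24 of 30 leave AML-free at one time, and one of them later has documented AML. The crude proportion is 1/30 = 3.3%, but the estimator gives 1/16 to 1/7, or 6.3% to 14.3% (assumed counts).
- Too low: AML in leavers goes undetected, or their deaths are counted while their AML-free time is not.

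The crude n/N discloses this but does not correct it. An optional sensitivity analysis could restrict AML events and deaths to a fixed interval after the last disease evaluation.

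**Cost.** A few sentences and one standard estimator. No new data, visits or eCRF items are needed, and no protocol amendment, since Protocol 11 leaves specific details to the SAP.

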4.1. Inclusion Criteria

Each potential subject must satisfy all of the following criteria to be enrolled in the study:

1. 18 years of age
2. MDS according to World Health Organization (WHO, [Attachment 1](#)) criteria confirmed by bone marrow aspirate and biopsy within 12 weeks prior to first dose. A local laboratory report from this diagnostic bone marrow aspirate and biopsy must be approved by the sponsor.
3. IPSS low risk or intermediate-1 risk MDS ([Attachment 2](#))

-
4. RBC transfusion dependent
 - Received at least 4 units of RBCs over any 8 consecutive weeks during the 16 weeks prior to randomization
 - Pretransfusion Hb must have been ≤ 9.0 g/dLSource documentation for transfusions verified by the sponsor.
 5. Relapsed/refractory to ESA treatment; the sponsor must verify this diagnosis as defined by meeting any of the criteria below:
 - Received at least 8 weeks of treatment with a minimum weekly dose of epoetin alfa 40,000 U, epoetin beta 30,000 U or darbepoetin alfa 150 mcg (or equivalent agent/dose) without having achieved a Hb rise ≥ 1.5 g/dL or decreased RBC transfusion requirement by at least 4 units over 8 weeks
 - Transfusion dependence or reduction in Hb by ≥ 1.5 g/dL after hematologic improvement, in the absence of another explanation
 - Endogenous serum EPO level > 500 mU/mLSource documentation for failure of ESA treatment verified by the sponsor
 6. Adequate iron stores, defined as transferrin saturation greater than 20% and serum ferritin greater than 400 ng/mL, measured within the screening period, or adequate iron stores as demonstrated by recent (within 12 weeks prior to first dose) bone marrow examination with iron stain.
 7. ECOG performance status 0, 1 or 2 ([Attachment 3](#))
 8. Hematology laboratory test values within the following limits:
 - ANC $\geq 1.0 \times 10^9/L$ (ie, $\geq 1,000/mm^3$) independent of growth factor support. For the screening ANC to be considered growth factor independent, a 7-day period after stopping the growth factor should be observed, or 7 half-lives of growth factor used, whichever is longer.
 - Platelets $\geq 50 \times 10^9/L$ independent of platelet transfusion support. For the screening platelets to be considered independent of platelet transfusion support, platelet count must be stable for 3-4 days after the transfusion.
 9. Criterion numbering modified per Amendment 2
 - 9.1 Biochemical laboratory test values must be within the following limits:

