6.1.2. HANDLING OF MISSING TRANSFUSION ASSESSMENTS

In order to be considered transfusion independent, a subject must have completed continuous transfusion assessments throughout the qualifying observation period where his/her transfusion independence is determined. An apparent transfusion free period with one or more missing transfusion assessments will not be considered a qualifying 8-week or 24-week TI period. Subjects with no qualifying observation periods will be considered non-responders. In addition, the number (%) of patients who have missed one or more visits will be tabulated.

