6.2. MAJOR SECONDARY ENDPOINTS

6.2.1. DEFINITION

24-Week RBC TI Rate

24-week RBC TI rate is defined as the proportion of subjects without any RBC transfusion during any consecutive 24 weeks (168 days) starting from Study Day 1 until the end of study. The starting date of 24-week RBC TI must be between Study Day 1 and End of treatment Phase ending date (date of last dose of study medication + 30 days).

Time to 8-Week (24-Week) RBC TI

Pertaining only to subjects who achieved TI, time to the 8-week (24-week) RBC TI is defined as the interval from Study Day 1 to the first day of the first 8-week (24-week) RBC TI period.

Duration of RBC TI

Pertaining only to subjects who achieved TI for at least 8 weeks, duration of RBC TI is defined as the maximal number of consecutive transfusion-free days that are ≥ 56 days (8 weeks). For subjects maintaining transfusion-free by the time of the cutoff date for the analysis or who withdraw from the study, duration will be censored at the date of the last transfusion evaluation. Duration of 24-week TI is defined similarly.

Rate of Hematologic Improvement per International Working Group Response Criteria 2006 (IWG 2006)

The IWG criteria for HI define specific responses of cytopenias in the three hematopoietic lineages: erythroid (HI-E), platelet (HI-P), and neutrophil (HI-N). Rate of hematologic improvement of erythroid lineage is the focus of this study, which is defined as the proportion of subjects who achieve HI-E.

HI-E is defined as a hemoglobin (Hb) rise of at least 1.5 g/dL above pretreatment and lasting at least 8 weeks or reduction of at least 4 units of RBC transfusions/8 weeks compared with the prior RBC transfusion burden. Pretreatment Hb level is defined as the average of all the Hb values in the 8 weeks prior to study entry, including the value on Cycle 1 Day 1 and excluding values that were within 14 days after transfusion (thus considered to be influenced by transfusion). If there were no Hb values that met this definition of not being influenced by transfusions, then the baseline value is used.

Rate of Complete Remission (CR) or Partial Remission (PR)

Defined as the proportion of subjects who achieve CR, or PR per IWG 2006 [4].

Overall Survival (OS)

OS is defined as the interval from Study Day 1 to death from any cause. Survival time of living subjects will be censored on the last date a subject is known to be alive or lost to follow-up.

Time to Progression to AML

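### The 8-week windows for transfusion reduction in SAP 6.2.1 need not be fully observed, so unobserved days can count as transfusion-free

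*SAP*

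**What the plan says.** **Transfusion amount and reduction.** SAP 6.2.1 counts RBC units in an "8-week (any consecutive 56 days period) interval during study". It takes as the best reduction the minimum "number of RBC transfusions in any post-baseline 8-week interval" and expresses it relative to the prior burden. The one explicit limit is on the start: "The starting date of a post-baseline 8-week interval must be between Study Day 1 and End of treatment Phase ending date", the latter being last dose + 30 days. Nothing is said about the end of the window, missing assessments, death, withdrawal or data cutoff.

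**Comparator.** The "prior RBC transfusion burden is the maximum number of RBC units transfused over an 8-week period during the 16 weeks prior to Study Entry". Protocol 4.1 sets a floor for it: "Received at least 4 units of RBCs over any 8 consecutive weeks during the 16 weeks prior to randomization".

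**HI-E.** The transfusion limb in SAP 6.2.1 is a "reduction of at least 4 units of RBC transfusions/8 weeks compared with the prior RBC transfusion burden". It does not say which 8 weeks are used or whether they must be complete. The 8-week durability wording in that sentence is attached to the hemoglobin limb.

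**TI.** SAP 6.1.2 is explicit: "An apparent transfusion free period with one or more missing transfusion assessments will not be considered a qualifying 8-week or 24-week TI period". It adds: "Subjects with no qualifying observation periods will be considered non-responders". Both sentences concern TI.

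**The concern.** Two measures built from the same transfusion record follow different rules. For TI, a gap in the record disqualifies the period. For transfusion reduction, a gap adds no units and so lowers the count. Because the lowest count is kept, the rule favours windows with the most unobserved time. The error can run only in the drug's favour, and it grows as follow-up of transfusions gets worse.

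Incomplete windows are foreseeable. A window starting on last dose + 30 days ends on last dose + 85 days (30 + 55). Protocol 9.2.1 collects post-treatment transfusions every 4 to 6 weeks, but the daratumumab Time and Events Schedule asks for this only where feasible. Protocol 8.2 names transfusions among the concomitant therapies, which are in general recorded to 30 days after dosing. A subject still on treatment at a data cutoff can also have a window that extends past the data.

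HI-E is the hematologic-improvement measure on which SAP 6.2.1 says the study focuses. SAP 3.4 gives other endpoints more weight when 6 or 7 subjects reach TI.

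**Working it through.** **1. The primary rule is not touched.** With a Beta(0.5+m, 0.5+30−m) posterior, the 10th and 90th percentiles reproduce SAP Table 1 for m = 4 to 14. For example, m = 5 gives (9.6, 26.8) and m = 8 gives (17.6, 37.9). P(rate ≤ 15% | 8/30) = 0.045 and P(rate ≥ 30% | 5/30) = 0.049, both below 10%. TI itself is governed by 6.1.2.

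**2. The contradiction.** Zero units in a fully observed 56-day window is 8-week TI by SAP 6.1.1, which has the same start-date limits. A 100% reduction in a TI non-responder can therefore come only from a window that was not fully observed. Since the prior burden is at least 4 units, a count of zero is also a drop of at least 4.

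**3. Illustration (assumed subject).** Prior burden 4; 2 units every 28 days from Day 10; no drug effect. Relative change = (units − burden)/burden.

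| Record ends | Last dose | Literal rule: window start, days observed, units | Full observation required |
|---|---|---|---|
| Day 40 | Day 29 | Day 39, 2 of 56, 0 units | no evaluable window |
| Day 70 | Day 57 | Day 67, 4 of 56, 0 units | 4 units |
| Day 100 | Day 85 | Day 95, 6 of 56, 0 units | 4 units |
| Day 169 | Day 155 | Day 151, 19 of 56, 0 units | 4 units |

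Under the literal rule every row gives (0 − 4)/4 = −100% and a 4-unit drop. With full observation, the evaluable rows give (4 − 4)/4 = 0% and no HI-E.

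**4. Size, by simulation.** Assumptions: no drug effect, 2 units per transfusion, last dose Day 168, and collection ending uniformly 0 to 86 days later. Baseline is the maximum 8-week total in the prior 16 weeks. HI-E is scored on the same minimum-count windows.

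- *False 100% best reduction:* about 40-51% of affected subjects across the gap patterns tried; 0% with full observation.
- *False HI-E, perfectly regular gaps* (every 28, 21 or 14 days; burden 4, 6 or 8): about 50%, 70% and 75%; 0% with full observation.
- *False HI-E, irregular gaps* (21-35, 14-42, 10-32 or 7-21 days): already about 58-78% in fully observed windows. Truncation adds about 17 to 28 percentage points across repeated runs.

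**5. Effect on the HI-E rate.** Assume 3 to 6 of 30 subjects are affected. Then 3 × 0.17 = 0.51 and 6 × 0.28 = 1.68 extra responders. As rates, 0.51/30 = 1.7% and 1.68/30 = 5.6%, or about 2 to 6 points.

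**The case against.** **Death and withdrawal may already be excluded.** The interval must lie within the study. Protocol 10.1 treats death or loss to follow-up as completing the study, and 10.2 lists loss and withdrawn consent as withdrawal. On that reading, a window running past those events is not an eligible 56-day interval. This is a fair reading and narrows the point. It does not deal with lapsed collection or missed assessments while the subject is on study. The SAP also bounds TI by the end of study, yet still needed 6.1.2.

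**Stopping drug is not enough.** A reader might infer that anyone who stops treatment gains a false response. The documents do not support that. Protocol 10.2 keeps such subjects on study, transfusion collection continues after treatment, and 9.2.1 plans active searching of other sources. The artefact needs a gap in the record.

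**HI-E does not say any interval or minimum.** That is correct. The limb leaves its interval open and sits under an IWG 2006 heading. Protocol Attachment 6 requires HI responses to last at least 8 weeks. That implies a whole period but does not say how unobserved days count. The HI-E consequence is therefore conditional on using the same windows.

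**Regular gaps exaggerate the effect.** This stands. The 50-75% figures, and a fall to 0% once windows are complete, hold for HI-E only if transfusions are perfectly periodic.

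**Conclusion.** The gap is real. Taken literally, SAP 6.2.1 lets partly observed windows supply the best transfusion reduction, and it can credit a 100% reduction to a subject whom 6.1.2 scores as a TI non-responder. That conclusion rests on the text alone.

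The size rests on assumptions about when collection ends, how regular transfusions are, and how many subjects are affected; the documents give none of these. The best-reduction result is the firmer one: about 40-51% of affected subjects, and none with full observation. The HI-E effect is conditional and modest, at about 2 to 6 points for 3 to 6 affected subjects of 30.

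Two larger conclusions do not follow. The primary TI decision is not biased by this. Complete windows would not remove all false HI-E either, because much of it comes from setting a maximum baseline count against a minimum post-baseline count. The endpoints are secondary and descriptive, so this is a clarification worth making before analysis and not a threat to the main result.

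**What to change.** Add to SAP 6.2.1: *Amount, relative change, best RBC transfusion reduction and the transfusion route of HI-E use only 56-day intervals that end on or before the last completed transfusion assessment and contain no missing transfusion assessment (as in 6.1.2). Subjects with no such interval are non-responders for the transfusion route of HI-E and are reported as not evaluable for best reduction, with their number given.*

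The cost is this addition to the SAP and reuse of the filter that the TI derivation already needs. A few early leavers will have no best-reduction value, and the HI-E rate may be slightly lower. The maximum-versus-minimum comparison is left as it is and should be kept in mind when HI-E is interpreted.
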